Hypothesis: Both interventions will result in significant improvement in patient-reported outcomes. We hypothesize that adipose-derived stem cells will provide superior outcomes.

Methods:

Participants / Outcome Measures / Sample size: Participants with symptomatic knee OA will be recruited from the sports medicine and orthopedics clinics, as well as advertising flyers within the clinic.

Inclusion / Exclusion Criteria

Inclusion criteria

Age 25-75 years

BMI < 40

Diagnosis of knee OA (primary and post-traumatic)

(Note: Participant may have OA in both knees, but only the most symptomatic knee will be treated as part of this trial so that patient reported outcomes are clearly defined for a single joint. The non-study knee may undergo all usual care prior to enrollment in the study, but no additional interventions can be performed during the course of the trial. If participant requires additional treatment, the participant will be unenrolled in the study).

Radiographic evidence of OA of the target knee (Kellgren-Lawrence grades 1-4)

Continued OA pain in the target knee despite at least 6 weeks of 1 of the following nonoperative treatments: activity modification, weight loss attempt, physical therapy, or NSAID / acetaminophen.

Knee Osteoarthritis Outcomes Score (KOOS)-Pain subscale 20-65

Working knowledge of English language (to be able to complete all outcome scores)

Ability to attend all follow-up appointments

Exclusion criteria

Isolated patellofemoral OA

3+ effusion of the target knee (stroke test grading system)

Significant (10 degree) valgus or varus deformities

Prior injection therapy:

Steroid injection in target knee in the last 3 months

Viscosupplementation in target knee in the last 6 months

PRP in the target knee in the last 1 year

Cellular treatments in index knee (bone marrow, amniotic suspensions etc) all time

Participation in any experimental device or drug study within 1 year before screening visit

Oral or IM steroids for last 3 months

Medical condition that may impact outcomes of procedure including:

anemia

thrombocytopenia

bleeding disorders

inflammatory disorders like rheumatoid arthritis, lupus

diabetes

any history of cancer (other than non-melanoma skin malignancies)

taking anticoagulants (aspirin, Plavix, eliquis, Xarelto, warfarin, lovenox)

Taking immunosuppressants, having a severe systemic infection

Previous cartilage repair procedure on the injured cartilage surface (ie, OATS, ACI, MFX)

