Previous surgery at the target knee within the past 1 year
Any degree of cognitive impairment.
OA of either hip
Pregnancy, lactating, or intent to become pregnant during treatment period
Gout
History of infection or current infection at the affected joint
Smoking

Sample Size Calculation:

A total of 88 (44/group) participants will complete this two-treatment parallel-design study. The probability is 80 percent that the study will detect a treatment difference at a two-sided 0.05 significance level, if the true difference between treatments is 9 units. This is based on the assumption that the standard deviation of the response variable is 15.

We will enroll 110 (55/group) participants to ensure that 88 complete their 6 month visit assuming 80% follow up at the primary endpoint of the study.

Outcomes and Follow Up

Demographics collected

Age

Body mass index

Race

OA grade (as determined by KL stage on x-rays)

MRI severity (only if MRI within 1 year exists; no additional MRI will be ordered if participant does not have it) as determined by MOAKS score

The following outcomes will be collected at baseline, 1, 3, 6, and 12 months.

Adverse events

KOOS

VAS Pain (with ADLs)

Tegner

Additional baseline only measures: knee pain diagram and the pain catastrophizing scale

Additional 6 and 12 month only measures: failure (defined by failure to improve KOOS-P score, desire to seek additional treatment including injections or surgery) with failure at 6 months representing the primary outcome variable.

Follow-up plan:

All participants' first visit will be standard of care to provide a medical evaluation and assess best treatment plan for that participant, regardless of candidacy for this study. This evaluation includes x-rays of their knees as a standard part of the evaluation. This will be billed through insurance. If they meet criteria and choose to enroll, their procedure and all follow up visits will be covered by the research study funds. The schedule will be as follows (by group):

PRP:

- 1) Baseline (at time of enrollment during initial clinical evaluation, billed to insurance as standard evaluation, RedCap surveys administered in clinic)
- 2) Injection (REDCap surveys in clinic)
- 3) 1 month (REDCap surveys in clinic)
- 4) 3 months (REDCap surveys in clinic)
- 5) 6 months (REDCap surveys in clinic)
- 6) 12 months (REDCap surveys in clinic)

Adipose:

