- 1) Baseline (at time of enrollment during initial clinical evaluation, billed to insurance as standard evaluation, RedCap surveys)
- 2) Injection
- 3) 2 weeks (in clinic wound-check, covered by research fund, no surveys)
- 4) 1 month (REDCap surveys in clinic)
- 5) 3 months (REDCap surveys in clinic)
- 6) 6 months (REDCap surveys in clinic)
- 7) 12 months (REDCap surveys in clinic)

Primary outcome: KOOS-Pain 6 months

Data will be housed in RedCap on a password protected, location secured medical center computer.

This study will utilize REDCap (Research Electronic Data Capture), a software toolset and workflow methodology for electronic collection and management of clinical and research data, to collect and store data. The Ohio State Center for Clinical and Translational Science (CCTS) Research Informatics Services will be used as a central location for data processing and management. REDCap provides a secure, web-based application that provides an intuitive data manipulation interface, custom reporting capabilities, audit trail functionality, real-time data monitoring/querying of participant records, and variations of data exporting/importing. REDCap is hosted by OSUWMC IT in the Ackerman Datacenter ([name])

REDCap instance is located on an internal OSUWMC network. Remote access to this network can be obtained over an encrypted VPN tunnel (AnyConnect). This VPN uses

Protocol: DTLS and Cipher: RSA_AES_128_SHA1. Background checks are performed on all staff that are on the network or obtaining VPN access.

Randomization

Participants will be randomized using randomization function available in RedCap.

Statistics

Continuous variables will be checked for normality and subsequently compared using either unpaired t-tests (for normally distributed data) or Mann-Whitney U test (for non-normally distributed data) at 6 months for the primary outcome. The variables will be analyzed again at 12 months..

After randomization, participants , medical staff and research team will note treatment arm allocation.

All participants will receive the following pre-procedural instructions

Avoid non-steroidal anti-inflammatories (NSAIDs) and aspirin for 14 days before the procedure.

No exercise the day before and the day of the procedure

Arrive to the procedure well-hydrated

Procedural Details

Platelet rich plasma

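### The 6-month failure definition omits treatment already received, so a participant treated again on the study knee before month 6 can be scored a success or dropped instead of being counted as failed.

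*Combined protocol and SAP*

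**What the plan says.** Outcomes and Follow Up lists failure among the "Additional 6 and 12 month only measures". Its components are failure to improve the KOOS-Pain score and "desire to seek additional treatment including injections or surgery". The two are separated by a comma, with neither *and* nor *or*. The same sentence gives the endpoint its role: "with failure at 6 months representing the primary outcome variable". The line after the visit schedules says something different: "Primary outcome: KOOS-Pain 6 months".

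The outcomes collected at baseline and at 1, 3, 6 and 12 months are adverse events, KOOS, VAS pain and Tegner. No item for further treatment received on the study knee is listed.

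The only rule on further treatment is in a note under Inclusion criteria about participants with OA in both knees. It says of the non-study knee that "no additional interventions can be performed during the course of the trial", and then: "If participant requires additional treatment, the participant will be unenrolled in the study". That last sentence names no knee. The plan does not say whether an unenrolled participant is still followed, is scored, or is left out. The Statistics section gives tests for continuous variables only, with no method for a failure proportion, for further treatment or for missing data.

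**The concern.** A participant who needed an injection or surgery on the study knee within six months of the study treatment is about as clear a treatment failure as this trial will see. The definition registers such a participant only through a pain score that the later treatment may have improved, or through a wish for treatment that the later treatment may have satisfied.

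If these participants are scored as successes or disappear from the comparison, the failure rate is understated. The understatement is larger, in percentage points, in the arm with more failures, provided that further treatment is equally common among failures in both arms. On the wording that makes failure primary, this affects the main result. On the wording that makes KOOS-Pain primary, it affects a secondary endpoint, and the plan still does not say how KOOS-Pain values after further treatment are handled.

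**Working it through.** **The plan's own figure.** Sample Size Calculation gives a difference of 9, SD 15, two-sided 0.05 and 80% power. n per group = 2 × (1.96 + 0.84)² × 15² / 9² = 2 × 7.84 × 225 / 81 = 43.6, so 44 per group and 88 completers; 88 / 0.80 = 110 enrolled. The figures reproduce. They are for a continuous outcome, so they neither support nor contradict this point.

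**One participant through the text.** Suppose an injection or surgery on the study knee at month 4. At month 6 KOOS-Pain is above baseline and the participant wants nothing more.
- KOOS-Pain component: not met.
- Desire component, asked at the visit: not met.
- With both unmet, the participant is not a failure whether the comma means *and* or *or*.
- If the unenrolment sentence covers the study knee, the participant has left the study and, unless followed anyway, has no month-6 result.

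**Size.** The documents give no failure rate and no rate of further treatment, so both are assumed. Let p be the true failure proportion in an arm, and s the share of those failures who were treated again and would meet neither component at month 6 (or, on the second reading, are unenrolled).
- Scored as success: observed rate = p(1 − s).
- Left out: observed rate = p(1 − s) / (1 − ps).

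With p = 0.45 and 0.25 (true difference 20 points) and the same s in both arms:

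| s | Scored as success | Difference | Left out | Difference |
|---|---|---|---|---|
| 0.10 | 40.5% vs 22.5% | 18.0 | 0.405/0.955 = 42.4% vs 0.225/0.975 = 23.1% | 19.3 |
| 0.40 | 27.0% vs 15.0% | 12.0 | 0.270/0.820 = 32.9% vs 0.150/0.900 = 16.7% | 16.3 |

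**Unequal shares.** The same rows, mixed:
- s = 0.40 in the higher-failure arm and 0.10 in the other: 27.0 − 22.5 = 4.5 points if scored as success; 32.9 − 23.1 = about 9.8 points if left out.
- The reverse: 40.5 − 15.0 = 25.5 points if scored as success; 42.4 − 16.7 = 25.7 points if left out.

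The distortion therefore has no fixed direction.

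**Power, second illustration.** Assume true failure of 50% versus 25%, 44 per group, and a two-sided 0.05 normal-approximation test of two proportions with pooled variance under the null. This test is also an assumption, since the plan names none. With every treated failure counted: (0.25 − 1.96 × 0.1032) / 0.0997 = 0.48, power 68%. With 10%, 20% and 30% of failures treated again in each arm (5%, 10% and 15% of the higher-failure arm):
- scored as success: differences 22.5, 20.0 and 17.5 points, power 61%, 54% and 46%;
- left out, with the arms reduced accordingly: differences 24.3, 23.4 and 22.3 points, power 65%, 62% and 58%.

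**The case against.** The strongest objection is the unenrolment sentence. Its wording is general, and it uses the same term for further treatment as the failure definition. If it covers the study knee, the month-4 participant never reaches a month-6 score, and asking about desire makes sense because desire is what can be measured in those who remain. This stands to the extent that a reader should not infer that such participants will necessarily be scored as successes. That is one of two readings. The other does not remove the problem: it takes likely failures out of the comparison because of their outcome.

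A second objection is that someone who obtained an injection plainly desired it. The definition sets no time window, so this reading is possible. But the text does not say it, and a participant asked at month 6 can honestly answer no.

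Three other inferences go beyond the documents:
- That a month-6 failure is reset at month 12. The plan only lists failure as a 6- and 12-month measure and is silent on carrying status forward.
- That the trial's main comparison is compromised. The primary outcome is stated in two ways, and both the sample size and the named tests are for a continuous variable.
- That desire should leave the endpoint. Nothing here requires that, and removing it could lower the failure rate by dropping participants who want treatment but have not had it.

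**Conclusion.** The point holds as a gap in the endpoint definition that the unenrolment sentence does not close. On neither reading is a participant treated on the study knee before month 6 explicitly counted as failed.

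Under the assumed 45% versus 25%, with equal shares of 10% to 40%, the loss is 2 to 8 points of a 20-point difference if these participants are scored as successes, and about 0.7 to 3.7 points if they are left out. The upper ends require that 40% of failures be treated again and, on the first reading, that all of them improve and want nothing more; the documents offer no support for or against that. With unequal shares the difference can shrink further or grow. The stated sample size is unaffected. Whether the primary result is affected depends on which primary-outcome statement governs.

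**What to change.** 1. Keep both existing components and add a third: any injection or surgery on the target knee received since the study injection. State that meeting the third alone is failure, whatever the current KOOS-Pain score.
2. Record it as one dated REDCap item at the planned 1, 3, 6 and 12 month visits.
3. Count anyone who meets it by month 6 as failed at both 6 and 12 months, including anyone unenrolled for this reason.
4. Reconcile the note under Inclusion criteria with the failure definition: state which knee the unenrolment sentence covers, and that outcome data are still collected and analysed for these participants.
5. Reconcile the two primary-outcome statements.

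The cost is protocol wording, one REDCap item at visits already planned, and a somewhat higher reported failure rate. No extra participants, visits or procedures are needed.

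### Does a survey listed at the PRP injection visit, but not at the adipose one, leave KOOS-Pain failure without a common starting score?

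*Combined protocol and SAP*

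**What the plan says.** All references are to the combined protocol and SAP.

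- **Outcomes and Follow Up**, covering adverse events, KOOS, VAS pain and Tegner: "The following outcomes will be collected at baseline, 1, 3, 6, and 12 months".
- **Follow-up plan, PRP list**: the first entry is "Baseline (at time of enrollment during initial clinical evaluation, billed to insurance as standard evaluation, RedCap surveys administered in clinic". The second is "Injection (REDCap surveys in clinic", with no instrument named.
- **Follow-up plan, adipose list**: the first entry is "Baseline (at time of enrollment during initial clinical evaluation, billed to insurance as standard evaluation, RedCap surveys". The second names the injection visit and nothing more. The third is "2 weeks (in clinic wound-check, covered by research fund, no surveys".
- **Failure**, measured at 6 and 12 months: "failure (defined by failure to improve KOOS-P score", or a wish for further treatment. The visit from which improvement is counted is not named. The same sentence ends "with failure at 6 months representing the primary outcome variable".
- A separate line after the schedules reads "Primary outcome: KOOS-Pain 6 months".
- **Statistics** compares the arms at 6 months by unpaired t-test or Mann-Whitney test, and again at 12 months. It mentions neither a baseline covariate nor a change score.
- **Compensation** pays a gift card at the injection visit and at the 1, 3, 6 and 12 month visits, without distinguishing the arms.

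**The concern.** Read side by side, the two schedules seem to measure the arms differently before follow-up starts. PRP participants have a survey on injection day and adipose participants apparently do not. The adipose list marks its 2-week visit as survey-free, so its silence at injection could be taken as either a slip or a real difference.

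This would matter through the failure outcome. Improvement in KOOS-Pain needs a starting score. If an analyst used the injection-day score in PRP and the enrolment score in adipose, any drift in pain between those visits would enter one arm only and look like a treatment effect. Because one sentence calls 6-month failure primary, the distortion could reach a main result.

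**Working it through.** **1. The plan's own figures.** Inputs from Sample Size Calculation: difference 9, SD 15, two-sided 0.05, power 80%.

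n per group = 2 × (1.960 + 0.842)² × 15² / 9² = 2 × 7.849 × 225 / 81 = 43.6, rounded up to 44. The total is 88, and 88 / 0.80 = 110 enrolled, or 55 per group. The figures reproduce. At 44 per group, power is 80.4% by the normal approximation and 79.5% by the noncentral t. An injection-day survey enters none of this.

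**2. Survey occasions.**

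| Visit | PRP list | Adipose list | Outcome list |
|---|---|---|---|
| Baseline (enrolment) | yes | yes | yes |
| Injection | yes, instruments not named | silent | not listed |
| 2 weeks | no such visit | explicitly none | not listed |
| 1, 3, 6, 12 months | yes (4) | yes (4) | yes (4) |
| Total | 6 | 5 | 5 |

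The whole mismatch is 6 − 5 = 1 occasion, so at most 55 × 1 = 55 survey sets in PRP. The adipose list and the outcome list agree with each other; one PRP line stands apart. Since that line names no instrument, it is not shown to conflict with the KOOS, VAS and Tegner schedule.

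**3. Slip or design?** The paid visits are injection and 1, 3, 6 and 12 months. These are exactly the post-baseline survey visits of the PRP list. The adipose 2-week visit, the one marked survey-free, is not on the payment list. The adipose list is also more abbreviated elsewhere: its baseline entry omits the note, present for PRP, that surveys are done in clinic. Payment is for time, so this is not proof, but it favours a line left incomplete over a deliberate difference between arms.

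**4. Which starting score?** A KOOS-Pain reference must be a scheduled KOOS score taken before treatment. The outcome list gives one such time, baseline. Both schedules define it identically, as enrolment, and both attach surveys to it. No text places KOOS at the injection visit in either arm. Scoring failure from the plan as written therefore uses the enrolment score in both arms.

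**5. Effect on the 6-month comparison.** The estimate is the difference between arms in 6-month KOOS-Pain. No pre-treatment score appears in it, so the shift is 0.

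**6. What misuse would do, on assumed values only.** Suppose KOOS-Pain change is normal with mean 10 and SD 15. Then P(no improvement) = Φ(−10/15) = 25.2%. Let the reference in one arm alone be s points higher, so that P = Φ(−(10 − s)/15):

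- s = 3 gives 32.0%; s = 5 gives 36.9%.
- s = −3 gives 19.3%; s = −5 gives 15.9%.

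Across assumed means of 10 to 15 and SDs of 15 to 20, shifts of 3 to 5 points move the rate by about 4 to 12 percentage points. The documents supply none of these means, SDs or shifts. The calculation shows only what a one-arm choice of reference could do, and the plan does not make that choice.

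**The case for a change.** The best case for a change is that enrolment and injection day are not interchangeable. Eligibility requires a KOOS-Pain score of 20 to 65, so enrolment scores are selected on range and a later score need not be. Before the procedure, participants are told to stay off NSAIDs for two weeks and to avoid exercise on the day before and the day itself. Allocation is known after randomization, so an injection-day survey could be answered with the arm in mind. An unnamed reference visit also leaves room to choose once the data are seen. Finally, whoever sets up the REDCap events must know whether adipose participants complete a survey that day.

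Much of this is true. The two visits could give different scores, and the plan would read better with the injection line matched and the reference visit named. But the argument needs an analyst to pass over the only scheduled pre-treatment KOOS, take a score the plan never says is collected, and do so in one arm. That would depart from the plan; the plan does not leave it open as a choice. The REDCap build is not visible in the documents and may already match across arms.

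The clash between failure and KOOS-Pain as primary outcome is a separate and larger matter. It lends this point no weight.

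**Conclusion.** The mismatch in wording is real, but no change to the plan follows. It is most likely a clerical omission in the adipose list, and a competent analyst would fill the unnamed reference visit in the obvious way, with the enrolment score in both arms.

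Its size is one survey occasion and at most 55 survey sets. The shift in the stated 6-month KOOS-Pain comparison is 0, and no sample-size figure changes. Failure scored from the scheduled baseline is measured the same way in both arms.

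This rests on two readings: that baseline means the enrolment visit, as both schedules state, and that any injection-day survey in PRP is not used as a starting score in that arm alone. The documents support the first directly, and nothing in them provides for the use that the second excludes. Matching the two injection lines at some later revision would be harmless housekeeping.

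### The only planned test of 6-month KOOS-Pain cannot use the roughly 22 of 110 participants expected to lack that score, and ignores baseline, 1- and 3-month scores: precision is forgone, and response-related loss that differs by arm goes uncorrected

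*Combined protocol and SAP*

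**What the plan says.** All references are to the combined protocol and SAP.

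- **Statistics.** After a normality check, continuous variables are to be "compared using either unpaired t-tests (for normally distributed data) or Mann-Whitney U test (for non-normally distributed data) at 6 months for the primary outcome", with the comparison repeated at 12 months. The section gives no repeated-measures model, baseline covariate, imputation, analysis population or missing-data sensitivity analysis.
- **Outcomes and Follow Up.** "The following outcomes will be collected at baseline, 1, 3, 6, and 12 months", and KOOS is on that list.
- **Sample Size Calculation.** "A total of 88 (44/group) participants will complete this two-treatment parallel-design study". Then: "We will enroll 110 (55/group) participants to ensure that 88 complete their 6 month visit", on the assumption of 80% follow-up.
- **Inclusion criteria, note on participants with OA in both knees.** Participants who need additional treatment are unenrolled. The note does not say whether this covers the study knee, the other knee or both.
- **End of the Statistics section.** Participants, medical staff and research team all know the allocation.
- **Primary outcome.** The line after the visit schedule names KOOS-Pain at 6 months. Outcomes and Follow Up names failure at 6 months as the primary outcome variable.

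**The concern.** A two-sample test at 6 months uses only people who have a 6-month score. That the others are excluded is an inference, but a firm one, because neither named test can take a missing value and no imputation is planned.

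Two things are at stake. First, baseline and early follow-up scores predict the 6-month score, so ignoring them gives a wider confidence interval than the collected data allow. Second, if people who respond poorly leave one arm more than the other, the remaining participants no longer form a randomised comparison. The protocol makes such loss plausible: allocation is known to everyone, the stated hypothesis favours adipose, and needing more treatment is itself a reason for removal.

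**Working it through.** **Inputs.** From Sample Size Calculation: two-sided 0.05, 80% power, "if the true difference between treatments is 9 units", "the standard deviation of the response variable is 15", 44 completers and 55 enrolled per arm. That section does not name the scale or time point; I take it as KOOS-Pain at 6 months. Assumed, because the documents give no correlations: baseline with follow-up b = 0.3–0.5; any two follow-up visits r = 0.6–0.8; SD 15 at every visit.

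**1. The plan's own figures.**
- n per arm = 2(1.960 + 0.842)² × 15²/9² = 43.6, so 44; total 88.
- 88/0.8 = 110 enrolled; 110 − 88 = 22 without a 6-month score.
- SE = 15√(2/44) = 3.20. Power = Φ(9/3.20 − 1.96) = 80.4% (79.5% by noncentral t).

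The stated figures reproduce.

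**2. Precision if loss is random.** Baseline adjustment alone gives SE = 3.20√(1 − b²). If the 22 leave after month 3, a likelihood-based model that also uses months 1 and 3 has variance 2 × 225(1 − b²)[R²/55 + (1 − R²)/44], where R² = 2ρ²/(1 + ρ) and ρ = (r − b²)/(1 − b²).

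Example, b = 0.3 and r = 0.6: ρ = 0.51/0.91 = 0.560; R² = 0.403; variance = 409.5 × (0.403/55 + 0.597/44) = 8.56; SE = 2.93.

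| b | r | Baseline only: SE, power | Baseline + months 1, 3: SE, power |
|---|---|---|---|
| 0.3 | 0.6 | 3.05, 84% | 2.93, 87% |
| 0.3 | 0.8 | 3.05, 84% | 2.83, 89% |
| 0.5 | 0.6 | 2.77, 90% | 2.69, 92% |
| 0.5 | 0.8 | 2.77, 90% | 2.59, 93% |

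A simulation of 4,000 trials per setting over the same ranges gave SE 2.7–3.0 and power 85–92%. Together these give SE about 2.6–3.0 and power about 85–93%.

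At b = 0.5, baseline removes 25% of the variance and the early visits a further 6–12%. At b = 0.3, baseline removes 9% and the early visits a further 8–14%. The contribution of the early visits depends on timing: if all 22 left before month 1 it would be nil, and the baseline-only column would apply.

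**3. Bias, true difference 9 at months 3 and 6.** If the lowest fraction q at month 3 leaves an arm, that arm's completer mean at month 6 rises by 15 × r × λ(q), with λ(q) = φ(z_q)/(1 − q), where z_q is the normal quantile at q. λ(0.2) = 0.350.

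- *Lowest 20% leave each arm:* the shifts cancel and the difference stays at about 9.0.
- *One graded rule in both arms* (odds of leaving multiplied by 2.5 per 10 points worse; loss 25% PRP, 15% adipose): 8.3 at r = 0.5, 8.0 at r = 0.7. With no true effect the same rule gives a bias of about 0. A sharp common threshold gives 6.8 to 6.1 for r = 0.6 to 0.8.
- *Only PRP loss follows the 3-month score,* about 80% retained per arm: 6.6–7.7 in simulation, with t-test power 56–67%. A sharp cut-off is the outer case: 9 − 15 × 0.6 × 0.350 = 5.9, or 4.8 at r = 0.8.
- *The same pattern in adipose only:* the shifts of 1.3–2.4 change sign, giving 9 + 1.3 = 10.3 to 9 + 2.4 = 11.4. The sharp cut-off gives 12.1 to 13.2.

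In the simulated cases with loss driven by the 3-month score, an analysis using that score returned about 9.0.

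**4. Limit of the remedy.** If the lowest 20% on the 6-month score itself leave PRP, completers give 9 − 15 × 0.350 = 3.75. A likelihood-based estimate gives 5.5–6.9: closer, but still biased.

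**The case against.** The strongest case for the plan is that the loss is already paid for: 110 are enrolled to obtain 88 completers, and 88 completers give the stated power. That stands. A reader might infer that the trial is underpowered, but the sample size figures do not support that. Inflation does nothing about bias, however.

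A reader might also infer that the test is biased whenever early non-responders leave. That is too strong: equal loss of the worst 20% from each arm leaves the difference at about 9. Nor do the documents say which arm would lose more poor responders, so the 6.6–7.7 range illustrates one pattern and does not predict a direction.

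Three further limits stand.
- The model's return to 9.0 holds by construction when loss depends only on observed scores.
- The documents do not say when losses occur, so not all 22 would necessarily be recovered; anyone lost before month 1 stays out of the model too.
- Eligibility restricts baseline KOOS-Pain to 20–65, which could push the baseline correlation below 0.3 and shrink that part of the gain.

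**Conclusion.** The point holds in a limited form. The gap itself is certain: the stated analysis uses neither baseline nor early follow-up scores and has no provision for the 20% loss the plan expects.

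The sizes rest on assumed correlations and exit rules. The precision cost is an SE of about 3.2 where about 2.6–3.0 looks attainable. Baseline adjustment supplies much of that gain, and more as its correlation rises; the early visits usually add less, though not when the baseline correlation is low and the follow-up correlation high.

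The bias is conditional on response-related loss differing between arms, through different exit rules or through a common score threshold combined with a real effect. It can run either way. The open-label design and the unenrolment rule make it plausible but do not show that it will occur. It would be wrong to conclude that the planned test must understate the adipose effect, or that a mixed model would remove all bias.

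**What to change.** In the Statistics section, make the primary analysis of KOOS-Pain a mixed model for repeated measures at 1, 3, 6 and 12 months. Terms: arm, visit, arm-by-visit, baseline KOOS-Pain and baseline-by-visit, with unstructured covariance. Include every randomised participant with at least one follow-up score, in the assigned arm. The primary estimate is the 6-month arm contrast with its 95% CI; the 12-month contrast comes from the same model.

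Keep the completer t-test as a secondary analysis. It does not probe the missing-data assumption, so add a sensitivity analysis for loss that depends on unobserved scores, for example delta-adjusted imputation by arm. State how any scores recorded after unenrolment enter the analysis.

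Separately, reconcile which 6-month outcome is primary, KOOS-Pain or failure. This model applies to KOOS-Pain.

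The cost is revised wording and slightly more analysis work. No extra participants, visits or data are needed.

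### The 6-month KOOS-Pain comparison takes no account of baseline KOOS-Pain, so a valid test gives up precision that a prespecified ANCOVA would recover from data already collected

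*Combined protocol and SAP*

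**What the plan says.** The Statistics section plans "unpaired t-tests (for normally distributed data) or Mann-Whitney U test (for non-normally distributed data) at 6 months for the primary outcome", with a repeat at 12 months. A normality check decides between the two tests. No covariate, regression model or mixed model appears anywhere in the document, and no change-from-baseline variable is defined.

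The baseline value is available. Outcomes and Follow Up lists KOOS under the statement "The following outcomes will be collected at baseline, 1, 3, 6, and 12 months". The inclusion criteria require "Knee Osteoarthritis Outcomes Score (KOOS)-Pain subscale 20-65".

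On randomization the plan says only "Participants will be randomized using randomization function available in RedCap". It states no stratification.

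Two further statements bear on the point:

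- The line after the follow-up schedules reads "Primary outcome: KOOS-Pain 6 months", but Outcomes and Follow Up describes a failure measure, "with failure at 6 months representing the primary outcome variable".
- The Sample Size Calculation takes a difference of 9 units and says "This is based on the assumption that the standard deviation of the response variable is 15". It does not say whether that variable is the 6-month score or the change from baseline.

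**The concern.** The same instrument is scored in the same knee at enrolment and at 6 months, so some of the spread in 6-month scores is probably predictable from the enrolment score. An unadjusted comparison leaves that spread in the error term. It also lets a chance difference between arms in baseline KOOS-Pain pass into the estimated treatment effect, in proportion to the baseline slope. These are two views of one loss: the unadjusted standard error already allows for chance baseline gaps, and adjustment removes that component.

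The sample size leaves no margin, since exact power at the planned number of completers is just under 80%. Prespecification matters here because, according to the Statistics section, participants, medical staff and the research team all know the allocation. If the arms turned out to differ at baseline, a decision at that stage to adjust would be open to challenge.

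**Working it through.** **Inputs from the Sample Size Calculation.** Difference 9, SD 15, two-sided 5% level, 80% power, 44 completers per group (88), 110 enrolled with 80% follow-up.

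**Assumptions not in the documents.** SD 15 is the SD of the 6-month score. The correlation r between baseline and 6-month KOOS-Pain is taken over 0.1 to 0.5, and the baseline SD (SDb) over 8 to 12.

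**1. The plan's own figure.** The normal approximation gives 44 per group with 80.4% power, and 88/0.8 = 110. The stated size is reproduced as a plain two-group calculation.

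**2. Unadjusted test, exact.**
- SE = 15 × √(2/44) = 3.198.
- Noncentral-t power on 86 df = 79.5%.
- 95% CI half-width = 1.988 × 3.198 = 6.36 points.

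**3. ANCOVA.** The residual SD is 15√(1 − r²), and SE = 15√(1 − r²) × √(2/44 + gap²/Sxx) on 85 df. Here gap is the difference in baseline means between arms and Sxx is the within-arm baseline sum of squares. The gap²/Sxx term is the cost of estimating the slope. Results are averaged over random gaps.

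| r | Residual SD | Power | CI half-width | Half-width before covariate cost |
|---|---|---|---|---|
| unadjusted | 15.00 | 79.5% | 6.36 | – |
| 0.1 | 14.92 | 79.4% | 6.36 | 6.33 |
| 0.2 | 14.70 | 80.6% | 6.27 | 6.23 |
| 0.3 | 14.31 | 82.6% | 6.10 | 6.07 |
| 0.4 | 13.75 | 85.5% | 5.86 | 5.83 |
| 0.5 | 12.99 | 89.1% | 5.54 | 5.51 |

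At r = 0 ANCOVA has 79.0% power, a loss of about half a percentage point. It breaks even near r = 0.1.

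**4. Validity.** In simulation (20,000 trials at each r from 0.2 to 0.5) both tests had type I error of 4.8-5.2%, and both estimates centred on the true difference of 9 (8.94-9.03). ANCOVA power was 80.5%, 82.6%, 85.1% and 89.6%. With no treatment effect, the sequence of normality check and then t-test or Mann-Whitney rejected in 4.5-5.4% of trials for normal, capped and skewed data.

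**5. The same loss seen as a baseline gap.** The part of the unadjusted estimate carried by baseline has SD r × 3.198, whatever the baseline SD. In 95% of randomizations it lies within 1.96 × r × 3.198 = 1.3, 1.9, 2.5 and 3.1 points either way at r = 0.2, 0.3, 0.4 and 0.5, against a target of 9.

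As an illustration, the SE of the baseline gap is SDb × √(2/44) = 1.71, 2.13 and 2.56 at SDb 8, 10 and 12. The chance of a gap above 4 points is then about 2%, 6% and 12%. Such a gap shifts the estimate by 4 × r × 15/SDb. At SDb 12 that is 1.5 points at r = 0.3 and 2.5 at r = 0.5; at SDb 8 it is 2.25 and 3.75.

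**6. Effect of the entry window.** Baseline was assumed normal with mean 45-55 and SD 12-20, then truncated to 20-65. An unrestricted r of 0.5 becomes about 0.32-0.44, and an r of 0.3 becomes about 0.18-0.26.

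**The case against.** The strongest reply is that nothing is broken. The planned test is valid and matches the sample size calculation. The gain rests wholly on an r that the documents do not give and that the entry window pulls down. At r = 0.2 it is worth about one percentage point of power and 0.1 points of half-width, and at r = 0 there is a slight loss. All of this stands. It limits the claim to efficiency and makes the r = 0.5 row the optimistic end. It does not remove the case for adjusting, because the worst case costs about half a percentage point of power.

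Three narrower objections:

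- **The baseline-gap figures add no second harm.** This is correct: they restate the variance gain. SDb 12 is also towards the top for a 20-65 window, since a uniform spread has SD 45/√12 = 13.0 and the truncated normals above give 9.0-11.9.
- **The tested variable might be change from baseline.** The plan does not exclude this, and the figures above would then not apply. The direction holds: with equal SDs at the two times, ANCOVA variance is (1 + r)/2 times that of a change score, apart from the small covariate cost.
- **Replacing the plan's choice of tests drops its provision for non-normal data.** This is minor, as ANCOVA with about 44 per arm tolerates moderate non-normality. The choice by normality check also leaves open whether the result is a difference in means or a shift in ranks, which a single model settles.

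**Conclusion.** The concern holds as a missed gain in precision, not as an error. The direction is firm: baseline adjustment uses data already in hand, keeps the 5% level, and cannot cost more than about half a percentage point of power. The size is uncertain. If SD 15 is that of the 6-month score, power at 44 per group rises from 79.5% to between 80.6% and 89.1% for r from 0.2 to 0.5, and the half-width falls from 6.4 to between 6.3 and 5.5 points. Given the entry window, the lower and middle parts of that range are more plausible than the top. The change should be made, but the trial's conclusion would be valid without it. If failure at 6 months is confirmed as the primary outcome, the point applies to KOOS-Pain as a secondary endpoint.

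**What to change.** First reconcile the two statements of the primary outcome. Then, for KOOS-Pain, replace the choice between t-test and Mann-Whitney with wording such as:

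> 6-month KOOS-Pain will be compared between arms by a linear model (ANCOVA) with arm and enrolment KOOS-Pain as terms, reporting the adjusted mean difference with its 95% confidence interval.

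- Name the enrolment score as the covariate. Both schedules list surveys at enrolment, but only the PRP schedule has "Injection (REDCap surveys in clinic"; the adipose schedule lists no surveys at the injection visit.
- Use the same model at 12 months, and for VAS pain and the other KOOS subscales, each with its own baseline.
- State whether SD 15 refers to the 6-month score or to the change.
- Keep 110 enrolled and treat the stated power as conservative.
- Date the change before any comparison of outcomes by arm is seen, since allocation is known to the research team.
- If failure is primary, state its analysis separately.

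The cost is one main sentence in the Statistics section once the primary outcome is settled. No new data, visits or patients are needed. Handling of the expected 20% loss to follow-up is a separate matter that this model does not resolve.
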